## List of Abbreviations

AE	adverse event
AESI	adverse events of special interest
AF	assent form
ALRI	influenza-associated acute lower respiratory infections
AR	adverse reaction
CI	confidence interval
CRF	electronic case report form
D	Day
DC	diary card
DCGI	Drug Controller General of India
dil	Dilution
FAS	full analysis set
FDA	Food and Drug Administration
GBS	Guillain-Barré syndrome
GCI	Global Clinical Immunology
GM	geometric mean
HA	Hemagglutinin
HAI	hemagglutination inhibition
HAU	hemagglutination units
ICF	informed consent form
ICH	International Conference on Harmonisation
LLOQ	lower limit of quantitation
LLT	lowest level term
MedDRA	Medical Dictionary for Regulatory Activities
mL	Milliliter
NDAC	New Drug Advisory Committee
NH	Northern Hemisphere
OPV	Oral Poliomyelitis Vaccine
PPAS	per-protocol analysis set
QIV	Quadrivalent influenza vaccine
RBC	red blood cell
SAE	serious adverse event
SafAS	safety analysis set
SAP	statistical analysis plan
SH	Southern Hemisphere
TIV	trivalent influenza vaccine
ULOQ	upper limit of quantitation

WHO

World Health Organization

## 1 Introduction

Influenza is a highly contagious, acute viral respiratory disease. It is typically characterized by the rapid onset of fever, myalgia, sore throat, and non-productive cough. Influenza can cause severe malaise, which lasts for several days. While influenza affects all age groups, the very young, older adults and persons with underlying health problems are at increased risk for complications.

In temperate regions of the world, influenza occurs in winter season, whereas in tropical countries like India, peak influenza activity is seen during rainy season with some activity throughout the year. North India demonstrated peak activity in winter and rainy seasons, Eastern and Western India demonstrated highest activity during rains and limited activity in winter and South India demonstrated a peak in the cooler season during rains.

Vaccination is currently the most effective protection against influenza. Current vaccines induce serum anti-hemagglutinin (HA) antibody for prevention of subsequent infection and illness from natural influenza. Serum anti-HA antibody is the most consistent correlate of immunity to influenza, in that serum hemagglutination-inhibition (HAI) titer correlates inversely with frequency of influenza illnesses among vaccinated persons. Annual vaccination is recommended for the elderly population as well as for all adults at higher risk for influenza complications or in close contacts of persons at higher risk. Moreover, vaccination against influenza is recommended for any adult who wants to reduce the risk of becoming ill with influenza or of transmitting it to others. Influenza vaccination of the elderly reduces the risk of serious complication or death by 70-85%. In 2003, the World Health Assembly urged Member States with influenza vaccination policies to increase vaccination coverage of all people at high risk and to aim a vaccination coverage of elderly people of at least 50% by 2006 and 75% by 2010.

Children aged < 5 years, and particularly those < 2 years of age, have a high burden of influenza. A systematic review of the global disease burden of influenza in children, representing studies on a total of around 8 million children < 5 years of age, estimated that in 2008, there were 90 million (95%, confidence interval [CI] 49–162 million) new cases of seasonal influenza, 20 million (95% CI: 13–32 million) cases of influenza-associated acute lower respiratory infections (ALRI), and 1 to 2 million cases of influenza associated severe ALRI, including 28,000 to 111,500 deaths. The great majority of deaths from influenza occurred in developing countries.

Antigenic variation is an important feature of the influenza virus. To accommodate for this variation, since 1978, the use of trivalent influenza vaccines (TIVs) containing 1 H1N1 strain, 1 H3N2 strain and 1 B strain has been the norm. Fluzone® (Influenza Virus Vaccine), an inactivated TIV, has been used in the US since 1947, first as a whole virus preparation, and since 1980 as a split virus preparation, with a very good safety profile.

Unfortunately, the ability to predict with acceptable accuracy which B lineage will be dominant during an upcoming season has been unsatisfactory, with frequent mismatches between the lineage chosen for inclusion in the vaccine and the predominant lineage in circulation. Consequently, there seems to be growing evidence among regulators, industry, and academic advisors that the time has come to move toward a Quadrivalent influenza vaccine (QIV), which would add an additional alternate-lineage B strain to the current TIV.

In this context, Sanofi Pasteur has developed an inactivated quadrivalent influenza vaccine (QIV) containing 15 µg of HA of the two A strains (A/H1N1 and A/H3N2) and 15 µg of the two B strains (from the Victoria lineage and from the Yamagata lineage), based on the same manufacturing process as Fluzone manufactured by Sanofi Pasteur, US for active vaccination of subjects from 6 months of age (a pediatric formulation containing 7.5 µg of HA has been also developed).

Sanofi Pasteur conducted 3 studies (GRC43, QIV03, and QIV04) to evaluate the safety and immunogenicity of vaccination with QIV in adults and children (from 6 months of age). In these clinical trials, QIV demonstrated non-inferiority of antibody responses for each of the common 3 strains as compared to TIVs in each age group. QIV also demonstrated superiority of antibody response to the TIV groups which did not contain corresponding B strain in each age group. In addition, the overall safety profiles were similar in Fluzone® Quadrivalent and Fluzone groups in all age groups tested.

On June 7, 2013, US Food and Drug Administration (FDA) approved Sanofi Pasteur request to supplement the biologics license application for Influenza Virus Vaccine to include a Quadrivalent influenza virus vaccine formulation (Fluzone Quadrivalent) for use in persons 6 months of age and older (1).

This Quadrivalent vaccine is currently marketed in the US, Canada, Guatemala, Mexico, Panama, Venezuela, Hong Kong, and Malaysia. This vaccine is planned to be marketed during Southern Hemisphere (SH) 2015 influenza season in some other countries in Latin America and Asia.

## **2 Trial Objectives**

### **2.1 Immunogenicity Objective**

To describe in each age group the immune response induced by a single injection (subjects aged 9 years or older) or 2 injections (subjects aged 6 months to 8 years) of QIV

The endpoints for the immunogenicity objective are presented in Section 4.1.1.

### **2.2 Safety Objective**

To describe in each age group the safety profile of QIV

The endpoints for the safety objective are presented in Section 4.2.2.

### 3 Description of the Overall Trial Design and Plan

#### 3.1 Trial Design

This will be an open-label multi-center trial. A total of 400 subjects aged 6 months or older will be included in 4 age groups: 6 to 35 months, 3 to 8 years, 9 to 17 years, and 18 years or older (100 subjects per age group).

Subjects will be sequentially enrolled as follows:

Per requirement from New Drug Advisory Committee (NDAC) / Subject Expert Committee (SEC) and approval letters from the Drug Controller General of India (DCGI) dated 22 July 2014, 15 May 2015, and 17 August 2015, the following recruitment will be performed: 100 adult subjects (18 years and older) will be enrolled first to receive QIV injection.

The safety events (line listings) with an occurrence within 28 days after vaccination will be submitted to the DCGI for evaluation by SEC experts.

When the DCGI gives the Go decision, the younger age groups will be sequentially enrolled, as follows: firstly the 100 subjects from the 9 to 17 years group, secondly the 100 subjects from the 3 to 8 years group, and thirdly the 100 subjects from the 6 to 35 months group.

Safety events (line listings) with an occurrence within 28 days after vaccination for subjects aged 9 to 17 years and 28 days after the first vaccination for subjects aged 3 to 8 years will be reviewed by the Sponsor, and then submitted to the DCGI for information before moving to each of the younger age groups (3 to 8 years and 6 to 35 months).

All subjects will be vaccinated with the QIV (split-virion, inactivated) formulation recommended by the WHO Northern Hemisphere (NH) or SH according to the study timelines, by the intramuscular (IM) route.

The vaccination regimen will be as follows:

100 previously unvaccinateda subjects aged 6 to 35 months will receive 2 injections 4 weeks apart (28 days) of QIV 7.5µg HA/strain (0.25 milliliters [mL])

100 previously unvaccinated subjects aged 3 to 8 years will receive 2 injections at least 4 weeks apart (28 days) of QIV 15µg HA/strain (0.5 mL)

200 subjects aged 9 years or older (i.e., 100 adolescents aged 9 to 17 years and 100 adults aged 18 years or older) will receive 1 injection of QIV 15µg HA/strain (0.5 mL)

Immunogenicity of the vaccine will be assessed at baseline (Day 0 [D0]) and 28 days after the last injection. Safety data will be collected up to 28 days after each vaccination. Serious adverse events (SAEs), including adverse events of special interest (AESIs) will be collected throughout the trial (i.e., up to 28 days after the final vaccination).

---

a “previously unvaccinated”: a child aged 6 months to 8 years not adequately primed, e.g., if he / she has not been vaccinated with 2 doses (with an approximate interval of 4 weeks) for at least 1 previous influenza season, then 2 doses of influenza vaccine will be administered

## 3.2 Trial Plan

The trial plan is summarized in the Tables of Study Procedures (see Table 3.1 and Table 3.2).

### ***Recruitment and information of subjects / parents / legally acceptable representatives:***

Prior to enrollment, the investigator or a designee will inform subjects / parents / legally acceptable representatives of potentially eligible subjects about the trial. They will explain to subjects / parents / legally acceptable representatives that they may have to first sign an assent form and/or informed consent form (ICF) for Audio-Video Recording, if required by local regulation.

Then, candidates will be given a verbal description of the trial design, including but not limited to, the potential risks and benefits, discomforts, and subject responsibilities. Subjects / parents / legally acceptable representatives must voluntarily sign an ICF prior to enrollment in the trial. AFs may be voluntarily signed by the subject in accordance with local EC requirements or local regulations.

### ***Trial description and enrollment of subjects:***

After the subjects / parents / legally acceptable representatives (if applicable) have signed the ICF and, if applicable after the subject has signed the AF, and following confirmation by the Investigator that the subject has satisfied all inclusion / exclusion criteria, eligible subjects will be included in the study. They will provide their first blood sample (BL) and will be vaccinated with QIV.

### ***Sequential approach***

Per requirement from NDAC and approval from DCGI, adult subjects (18 years and older) will be enrolled first to receive QIV injection and will be followed for safety assessment. The younger age groups will then be enrolled sequentially when DCGI gives the Go decision as follows: firstly adolescents aged 9 to 17 years, secondly children aged 3 to 8 years, and then infants and toddlers aged 6 to 35 months (see Section 3.1 for more details).

### ***Vaccination***

Depending on their age, the subjects will receive 1 or 2 doses of QIV as follows:

Subjects aged 6 to 35 months will receive 2 injections 28 days apart of QIV 7.5µg HA/strain (0.25 mL)

Subjects aged 3 to 8 years will receive 2 injections 28 days apart of QIV 15µg HA/strain (0.5 mL)

Subjects aged 9 years or older will receive 1 injection of QIV 15µg HA/strain (0.5 mL)

### ***Blood sampling***

All subjects will provide a pre-vaccination baseline blood sample (3 or 5 mLa) at D0 and a second blood sample (3 or 5 mLa) 28 days after the last vaccination.

---

a 3 mL for subjects aged 6 months to 11 years and 5 mL for subjects aged 12 years or older

*Collection of safety data*

Solicited reactions from D0 to D7 and non-serious unsolicited adverse events (AEs) from D0 to D28 will be collected after each vaccination.

Information on SAEs, including AESIs, will be collected throughout the study.

**Table 3.1: Table of Study Procedures for Subjects Aged 6 Months to 8 Yearsa**

Phase III Trial, 3 Visits, 2 Vaccinations, 2 Blood Samples

Visit	V01	Phone Call or Home Visit	V02	Phone Call or Home Visit	V03
Trial timelines (days)	D0	V01 + 3 days	V01 + 28 days	V02 + 3 days	V02 + 28 days
Trial windows (days)	-	+2	± 2	+2	± 2
Indicative Months (M)			M1		M2
Informed consent / assent forms signed and dated	X				
Inclusion / exclusion criteria	X				
Demographics	X				
History of seasonal influenza vaccination / history of influenza diagnosis*	X				
Significant medical history	X				
Physical examination	X		X		X
Temperature (axillary)	X		X		
Temporary and definitive contraindications			X		
Assign subject number	X				
Blood sampling (3 mL)	BL1†				BL2
Vaccine injection	VAC1		VAC2		
30-minute surveillance period	X		X		
Diary Card (DC): Provided Collected	DC1		DC2 DC1		DC2
Contact with Subjects‡		X		X	
Recording of solicited injection site & systemic reactions			X		X
Recording of unsolicited non-serious adverse events			X		X
Reportable concomitant medication	X		X		X
Termination record					X
Serious adverse events§	Collected throughout the trial				

a ‘6 months to 8 years’ means from the day of the 6th month after birth to the day before the 9th birthday

- \* History of seasonal influenza vaccination and influenza diagnosis will be collected within the past 3 years or since birth for subjects aged 6 to 35 months
- † Collection of the first blood sample (BL1) will be before vaccination
- ‡ Telephone Calls or Home Visits:: trial personnel will ensure correct completion of DC, ask the subjects / subject's parent(s) / legally acceptable representative(s) whether the subject experienced any SAEs not yet reported, confirm the next visit and remind the subjects / subject's parent(s) / legally acceptable representative(s) that the DC should be brought to the trial center at the next visit
- § Including all AESIs

**Table 3.2: Table of Study Procedures for Subjects Aged 9 Years or oldera**

Phase III Trial, 2 Visits, 1 Vaccination, 2 Blood Samples

Visit	V01	Phone Call or Home Visit	V02
Trial timelines (days)	D0	Visit 1 + 3 days	Visit 1 + 28 days
Trial windows (days)	-	+2	± 2
Indicative Months (M)			M1

Informed consent / assent forms signed and dated	X		
Inclusion / exclusion criteria	X		
Demographics	X		
History of seasonal influenza vaccination / history of influenza diagnosis*	X		
Significant medical history	X		
Physical examination	X		X
Temperature (axillary)	X		
Urine pregnancy test†	X		
Assign subject number	X		
Blood sampling (3 or 5 mL‡)	BL1§		BL2
Vaccine injection	VAC1		
30-minute surveillance period	X		
Diary Card (DC) Provided Collected	DC1		DC1
Contact with Subjects**		X	
Recording of solicited injection site & systemic reactions			X
Recording of unsolicited non-serious adverse events			X
Reportable concomitant medication	X		X
Termination record			X
Serious adverse events††	Collected throughout the trial		

\* History of seasonal influenza vaccination and influenza diagnosis will be collected within the past 3 years

† For women of childbearing potential, the urine pregnancy test is to be performed before vaccination.

‡ 3 mL for subjects aged 9 to 11 years and 5 mL for subjects aged 12 years or older

a '9 years or older' means from the day of the 9th birthday

## 450 – Quadrivalent Influenza Vaccine

§	Collection of the first blood sample (BL1) will be before vaccination
**	Telephone Calls or Home Visit: trial personnel will ensure correct completion of DC, ask the subjects / subject's parent(s) / legally acceptable representative(s) whether the subject experienced any SAEs not yet reported, confirm the next visit and remind the subjects / subject's parent(s) / legally acceptable representative(s) that the DC should be brought to the trial center at the next visit
††	Including all AESIs

## 4 Endpoints and Assessment Methods

### 4.1 Immunogenicity Endpoints and Assessment Methods

See Section 9.1 of the protocol.

#### 4.1.1 Immunogenicity Endpoints

Immunogenicity will be evaluated before and 28 days after the final vaccinationa using the HAI technique. For each vaccine strain, serum HA antibody titers will be expressed as geometric mean (GM) of HAI titers obtained in duplicates for pre- (D0) and post-vaccination (28 days after the final vaccinationa).

The derived endpoints will be:

Individual geometric mean of duplicate titers (GM of titers) pre- and post-vaccination

Detectable HAI: titer  $\geq 10$  (1/dilution [1/dil]) pre- and post-vaccination

Individual titer ratio post-vaccination/pre-vaccination

Seroconversion status: titer  $\geq 40$  (1/dil) pre- and post-vaccination

Seroconversion or significant increase status:

- Seroconversion status: pre-vaccination titer  $< 10$  (1/dil) and post-vaccination titer  $\geq 40$  (1/dil)
- Significant increase status: pre-vaccination titer  $\geq 10$  (1/dil) and  $\geq 4$ -fold increase of post-vaccination titer

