#### 4.1.2 Immunogenicity Assessment Methods

Anti-HA antibody titers will be measured using the HAI method from the sera obtained on D0 and D28 after the last vaccinationa, according to a reference technique. For each vaccine strain, samples obtained pre- and post-vaccination from a same subject will be tested simultaneously in

a D56 for subjects aged 6 months to 8 years, and D28 for subjects aged 9 years and older

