#### 4.3.2.2 Seroprotection

If the computed value is  $\geq 1:40$  1/dil, then the derived seroprotection indicator will be “Yes” for that test, otherwise seroprotection will be “No”. If the computed value is missing, seroprotection will be missing.

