#### 4.3.2.4 Seroconversion

Seroconversion is defined as either

- a computed value  $< 10$  1/dil at D0 and post-injection computed value  $\geq 40$  1/dil at D28 or
- a computed value  $\geq 10$  1/dil at D0 and a  $\geq 4$ -fold increase in computed titer values 1/dil at D28 as described in Section 4.3.2.3.

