**Table 5.1: Descriptive statistics produced**

Baseline characteristics and follow-up description	Categorical data	Number of subjects. Percentage of subjects.
	Continuous data	Mean, standard deviation, quartiles, minimum, and maximum.
Clinical safety results	Categorical data	Solicited: Number and percentage (95% CIs) of subjects. Unsolicited: Number and percentage (95% CIs) of subjects, and number of events.
Immunogenicity results	Categorical data (seroprotection, seroconversion, cutoff)	Number and percentage (95% CIs) of subjects.
	Continuous data (titer / data†)	Log10: Mean and standard deviation. Anti-Log10 (work on Log10 distribution, and anti-Log10 applied): Geometric mean, 95% CI of the geometric mean, quartiles, minimum, and maximum. Graphical representation by Reverse Cumulative Distribution Curve (RCDC).

The confidence interval (CI) for the single proportion will be calculated using the exact binomial method (Clopper-Pearson method, quoted by Newcombe (2)), i.e., using the inverse of the beta integral with SAS.

For immunogenicity results, assuming that Log10 transformation of the titers follows a normal distribution, at first, the mean and the 95% CI will be calculated on Log10 (titers) using the usual calculation for normal distribution (using Student's t distribution with n-1 degree of freedom), then antilog transformations will be applied to the results of calculations, in order to provide GMs and their 95% CI.

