#### 5.1.1.2 Statistical Methods

The following parameters will be presented:

GM of titers on pre-vaccination (D0) and post-vaccination (D28/D56a)

GM of titers ratio D28/D0 or D56/D0

Rate of subjects with titer  $\geq 10$  (1/dil) on D0 and D28 or D56

Seroprotection rate (titer  $\geq 40$  [1/dil]) on D0 and D28 or D56

Seroconversion or significant increase rate from D0 to D28 or D56

Immunogenicity analyses will be performed according to the following age sub-groups following the schedule applied:

- 6 to 35 months
- 3 to 8 years
- 9 to 17 years
- 18 years or older: additionally a subgroup analysis will be done on 18 to 64 years, and 65 years and older

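### Does the wrong name on the titer ≥ 40 endpoint in SAP 4.1.1, with the bare D28 in 4.3.2.4, call for a change to the plan?

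*SAP*

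**What the plan says.** Section 4.1.1 lists five derived immunogenicity endpoints: the individual geometric mean of duplicate titers, detectable HAI (titer at least 10), the post/pre titer ratio, an item for titer at least 40, and seroconversion or significant increase. The fourth opens "Seroconversion status: titer" and applies its threshold of 40 both before and after vaccination. The fifth has a sub-item that opens "Seroconversion status: pre-vaccination titer" and requires a value below 10 before vaccination and at least 40 after it.

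Other sections treat the 40 threshold as follows:

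- Section 4.3.2.2: if the computed value is at least 40, "then the derived seroprotection indicator will be" set to Yes.
- Section 5.1.1.2: "Seroprotection rate (titer" at least 40) is presented at D0 and at D28 or D56, as a separate line from the seroconversion or significant increase rate.
- Table 5.1: "Categorical data (seroprotection, seroconversion, cutoff") keeps the two terms apart.

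On timing, both branches of section 4.3.2.4 name D28. The second, for subjects with a detectable baseline titer, asks for a four-fold "increase in computed titer values 1/dil at D28 as described in Section 4.3.2.3". The footnote to section 4.1.2 gives the sampling day as "D56 for subjects aged 6 months to 8 years, and D28 for subjects aged 9 years and older". Table 3.1, for the younger subjects, is headed "Phase III Trial, 3 Visits, 2 Vaccinations, 2 Blood Samples"; it puts the samples at Visits 1 and 3 and none at Visit 2.

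**The concern.** Within one list, a single term carries two rules that do not agree. The first is a status at a single time point; the second is a change between two. Section 2.1 sends the reader to 4.1.1 for the endpoints, and the word seroprotection does not appear there. Someone who built table shells from 4.1.1 alone could head a column seroconversion and fill it with the share of subjects at or above 40. In a descriptive trial the named rates are the results, so a wrong heading would misreport what the vaccine did. A subject already at 80 before vaccination and still at 80 afterwards would count under that heading without having responded.

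The D28 wording looks like a second fault of the same kind. Read as a study day, it points the seroconversion rule for the two youngest age groups to the second-vaccination visit, where no blood is drawn.

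**Working it through.** The SAP states no figure that depends on this point, so the check is mainly a comparison of passages.

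**Do the two rules called seroconversion in 4.1.1 differ?** Take rule A as a post-vaccination titer of at least 40. Take rule B as below 10 before and at least 40 after, or at least 10 before with a rise of at least four-fold.

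| Pre | Post | A | B |
|---|---|---|---|
| 5 | 40 | yes | yes |
| 20 | 40 | yes | no (2-fold) |
| 80 | 80 | yes | no (1-fold) |
| 80 | 320 | yes | yes (4-fold) |

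On the two-fold scale from 5 (half the LLOQ) to 10240 there are 12 possible titers, hence 12 × 12 = 144 pre/post pairs. Nine of the 12 titers are at least 40, so A holds in 12 × 9 = 108 pairs. B holds in 9 + 9 + 8 + 7 + 6 + 5 + 4 + 3 + 2 + 1 = 54 pairs, all of them among the 108. The rules therefore disagree in 108 − 54 = 54 pairs. This is an unweighted count of possible pairs. It shows that the name matters, but it does not estimate how many subjects would be misclassified.

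**Can the intended reading be recovered?**

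- The misnamed item carries its own threshold and time points, so what is computed is clear whatever it is called.
- It is evaluated before vaccination as well as after. Seroconversion needs two samples, so it cannot exist before vaccination; the label refutes itself.
- Sections 4.3.2.2 and 4.3.2.4 derive two separate variables under the right names, and 5.1.1.2 reports them on two separate lines.
- With the fourth item read as seroprotection, the five items in 4.1.1 match the five parameters in 5.1.1.2 one to one, with none left over.

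**Can D28 select a wrong titer?**

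- In Table 3.1, Visit 2 is D28 ± 2, that is D26 to D30, with the second vaccination and no blood draw.
- Visit 3 is Visit 2 + 28 ± 2. The sample therefore falls at 28 + 28 = D56, at the earliest 26 + 26 = D52 and at the latest 30 + 30 = D60.
- The groups concerned are 6 to 35 months (100) and 3 to 8 years (100), 200 of 400.
- These subjects have one baseline and one post-vaccination sample. A program that looks for a post-vaccination titer finds the Visit 3 value or nothing.
- The SAP often counts D28 from an injection: section 4.1.2 counts it from the last vaccination, section 3.2 collects unsolicited events to D28 after each vaccination, and section 5.6 counts it from the first vaccination. On the 4.1.2 usage, D28 in 4.3.2.4 is the scheduled sample for every age group.
- The fold-rise rule in 4.3.2.3, to which 4.3.2.4 refers, speaks only of baseline and post-baseline values. Section 5.1.1.2 gives D28 or D56, and the per-protocol rule in 5.2.2 names Visit 3 for the younger subjects.

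**The case for a change.** The best case for a change is that the SAP gives no order of precedence between 4.1.1 and 4.3.2, that the stated objective points to 4.1.1, and that the trial reports nothing but descriptive rates, so each rate should carry one name throughout. Section 4.3.2.4 uses D0 in the same sentences, which favours reading D28 as a study day, and it lacks the footnote found elsewhere. Correcting both would be a matter of words, with no programming cost.

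Much of this is true. The label is wrong, it is not an artefact of text extraction, and the two rules do separate subjects. The absence of a precedence rule carries little weight, because the sections do not compete over what to compute: 4.1.1 gives the same threshold and time points as 4.3.2.2 and 5.1.1.2 and differs only in the name. The D28 argument is weaker still. A day without serum cannot yield a wrong titer, and applied literally the rule would leave two age groups with no seroconversion result, which any programmer would notice and resolve from 5.1.1.2. What remains is a small chance of a wrong heading copied from 4.1.1, and a reader who set it beside Table 5.1 or 5.1.1.2 would see it.

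**Conclusion.** No change to the plan follows. Section 4.1.1 misnames one of its five derived endpoints, and 4.3.2.4 omits the D56 qualifier that the SAP states elsewhere. Both are clerical slips whose meaning the same document settles. On the intended reading no subject's seroprotection or seroconversion status changes. The FAS and PPAS definitions, the sample size of 100 per age group and the interval widths in Table 5.2 do not depend on either wording, and no hypothesis is tested that a label could affect.

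This rests on two assumptions: that outputs are built from the derivation rules in 4.3.2 and the parameter list in 5.1.1.2, as is usual, and that subjects aged 6 months to 8 years give the two samples scheduled in Table 3.1 and no other. Were an extra sample taken from them around D28, the bare D28 in 4.3.2.4 would become a real ambiguity; the schedule provides for none.
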